#### 1.10 Timetable/Schedule of Events

	Jul 2017	Aug 2017	Sep 2017	Oct 2017	Nov 2017	Dec 2017	Jan 2018	Feb 2018	Mar 2018	Apr 2018	May 2018	Jun 2018
Rutgers / NBHA project meeting	X		X		X		X		X		X	X
Train study therapist & research asst.	X	X										
Recruit participants (N=60; 2/week)			X	X	X	X	X	X	X			
Complete follow up assessments				X	X	X	X	X	X	X		
Data analysis										X	X	

**2.2 Resources Available**

**Facilities**-[name] has laboratory space at both the Institute for Health and Tillett Hall where RAs will prepare study materials, conduct phone screens, schedule participants, complete reminder calls/texts/emails, store study materials, and manage data entry. In addition, [name] has similar space located in the Division of Addiction Psychiatry, Rutgers RWJMS at [name] in New Brunswick.

**Medical Or Psychological Resources**- Both Drs. [name] and [name] are licensed clinical psychologists in the state of New Jersey and will assist in training study staff in the management of crisis intervention. In addition, they will be available 24/7 to field any questions/concerns study staff have regarding how to proceed in the event that participants experience unanticipated psychiatric distress during the course of the study.

**Research Staff Training**- All graduate students and research assistants will complete intensive training with the Drs. [name] and [name], including proper administration of each intervention condition and proper administration and management of nicotine replacement therapies. Training will include didactic instruction, as well as mock-administration of the interventions with structured feedback. All graduate students will also complete weekly supervision with Drs. [name] and [name].

**3.0 Multi-Site Research Communication & Coordination**

N/A

Protocol version: 03.15.2019

PI Name: [name].

Protocol Title: Addressing Tobacco Among  
Public Housing Residents

11

RESERVED FOR IRB STAMP  
DO NOT MODIFY THIS SPACE

IRB ID: Pro20170000679

IRB Form Version: y120116

3/25/2019

Approval Date:

3/24/2020

Expiration Date:

### **3.1 Outside Research**

N/A

### **4.0 Research Data Source/s**

#### **4.1 Primary Data-Subjects and Specimens**

Research participants will be 60 daily socioeconomically disadvantaged smokers receiving services at a New Brunswick, NJ based agency. We will collect questionnaire data and expired breath carbon monoxide.

#### **4.2 Subject Selection and Enrollment Considerations**

##### **A. Recruitment Details**

Research assistants will post flyers and place leaflets at New Brunswick, NJ social service agencies and will work with staff at said agencies for help in connecting with potential participants.

##### **B. Source of Subjects**

Service agencies in New Brunswick, NJ (e.g., New Brunswick Housing Authority, Elijah's Promise).

##### **C. Method to Identify Potential Subjects**

Research assistants will post flyers and place leaflets at New Brunswick, NJ social service agencies and will work with staff at said agencies for help in connecting with potential participants. Participants responding to flyers or otherwise referred will complete a "pre-screen" to determine likely eligibility. Those passing the pre-screen will be invited to participate in the study and complete the full baseline battery during which eligibility will be confirmed.

##### **D. Subject Screening**

Interested participants will complete a brief in-person or telephone screening where they will be assessed by trained study personnel who will determine initial eligibility.

##### **Inclusion Criteria**

Participants must be between the age of 19 and 65, must self-report being a daily smoker and provide biochemical verification of smoking status (expired breath carbon monoxide reading >5), must be at socioeconomic disadvantage, defined as receiving services at a New Brunswick, NJ based social services agency (i.e., living in New Brunswick Housing Authority-run public housing units or requesting social services from the community social service agency, "Elijah's Promise"), and must be able to speak and read English.

##### **Exclusion Criteria**

Exclusion criteria include taking FDA approved smoking cessation or anti-psychotic medications, self-reported medical issues of potential concern to nicotine replacement users (i.e., See Table 1, e.g., unstable angina pectoris, myocardial infarction, or significant cardiac arrhythmia (including atrial fibrillation) in the past 30 days), or self-reported pending legal issues with potential to result in incarceration. Additionally, using the not pregnant form, women must state in writing that they are not pregnant or nursing, planning on becoming pregnant in the next two months, and that they are using effective birth control.

##### **E. Recruitment Materials**

We will rely upon flyers and leaflets. Please see attachments. We additionally anticipate recruitment of participants via word-of-mouth.

### **4.3 Subject Randomization**

We will use a block randomization procedure to allocate participants to one of three groups. Block randomization is a procedure in which participants are randomly allocated to interventions groups within blocks such that an equal number are assigned to each intervention. We will use the Sealed Envelope Ltd. 2017 application to

electronically develop a list of 60 allocation outcomes using a block randomization procedure with 3 intervention groups and block sizes of 3, 6, and 9. A research assistant will use this list to create envelopes for therapists to open (revealing allocation to intervention) after each participant provides informed consent and is deemed eligible to participate in the study.

#### **4.4 Secondary Subjects**

N/A

#### **4.5 Number of Subjects**

##### **A. Total Number of Subjects**

N=64

##### **B. Require Number of Subjects to Complete Research**

N=60

#### **C. Feasibility Of Recruiting**

We anticipate enrolling 2-3 participants weekly over the course of 7 months. Based on previous research conducted by the principal investigators, and the reports from staff at Elijah's Promise, this should be feasible.

#### **4.6 Consent Procedures**

##### **A. Consent**

All participants will provide written informed consent after being given the opportunity to read the consent form in full and to ask questions about the research. A research assistant will also sign the consent form as a witness.

##### **B. Consent Process**

###### **Location of Consent Process**

Verbal consent will be obtained for the initial phone screen. The PI or RA will first explain the purpose of the phone screen and limits of confidentiality and provide an overview of the study. If potential participants remain interested, they must verbally agree to phone screen completion.

During the initial in-person meeting at our research offices, or at the agency at which the participant is associated, study personnel will verbally go over the consent form including details regarding the procedure, time commitment, payment, risks/benefits, and option to discontinue at any time without penalty, and ask the participant questions to ensure they understand.

###### **Individual Roles for Researchers Involved in Consent**

PI supervised/trained graduate students and research assistants will complete all aspects of the consent procedures.

###### **1. Consent Discussion Duration**

Staff will go over details regarding the procedure, time commitment, payment, risks/benefits, and option to discontinue the study at any time without penalty. We anticipate that it will take participants 5 minutes to read the consent and up to an addition 5 for staff to review relevant information.

###### **2. Coercion or Undue Influence**

Protocol version: 03.15.2019

PI Name: [name].

Protocol Title: Addressing Tobacco Among  
Public Housing Residents

13

RESERVED FOR IRB STAMP

DO NOT MODIFY THIS SPACE

IRB ID: Pro20170000679

IRB Form Version: y120116

3/25/2019

Expiration Date:

3/24/2020

During the consent process, staff will make clear to participants that regardless of their ability to make a cessation attempt, they will receive full compensation, and that early termination will result in payment for the portion completed (i.e., visit 1 only), and will not result in loss of ability to participate in future research.

### **3. Subject Understanding**

In addition to providing written informed consent, participants must verbally indicate that they understand the study procedures and that they have no further questions.

#### **4.7 Special Consent/Populations**

N/A

#### **4.8 Economic Burden and/or Compensation for Subjects**

##### **A. Expenses**

N/A

##### **B. Compensation/Incentives**

Participants will be compensated \$20 for their initial study visit and an additional \$40 for completion of the follow-up visit. Participants must complete all questionnaires and participate in the discussion at the first appointment to receive the \$20 at the first appointment and must complete all questionnaires at the second appointment 30 days later to receive the \$40. Participants will receive the \$20 for the first appointment even if they do not attend the second appointment.

#### **4.9 Risks to Subjects**

##### **A. Description of Subject Risk**

Risks are expected to be minimal for our proposed study procedures, and we do not anticipate that participants will experience any adverse consequences associated with participation in this research, aside from mild distress associated with answering questions about physical and mental health.

**Telephone pre-screening and Pre-visit Questionnaires.** Following a phone screen to determine basic eligibility requirements, participants will complete a battery of self-report indices as outlined above. Participants will be scheduled for their study appointment within one week.

##### **B. Procedures for Risks to Embryo, Fetus, and/or Pregnant Subjects**

N/A

##### **C. Risks to Non-Subjects**

N/A

##### **D. Assessment of Social Behavior Considerations**

###### **Reasonably Foreseeable Risks**

Study risks are minimal and include a small, temporary increase in distress as a result of the assessments; however, the methodologies employed have been utilized in many labs and clinical settings with hundreds of participants suffering from a range of psychopathology, and approved by as many IRBs.

##### **Risk Of Imposing An Intervention On Subject With Existing Condition**

N/A

##### **Other Foreseeable Risks**

Protocol version: 03.15.2019

PI Name: [name].

Protocol Title: Addressing Tobacco Among  
Public Housing Residents

14

RESERVED FOR IRB STAMP  
DO NOT MODIFY THIS SPACE

RUTGERS | eIRB  
APPROVED

IRB ID: Pro20170000679  
IRB Form Version: 120116

3/25/2019

Expiration Date: 3/24/2020

Our research team employs standard procedures to ensure confidential information about study participation is not disclosed. All data are linked to an arbitrary 3-digit study ID unrelated to personal information. The file linking participants to their study ID will be stored in a password-protected file, located within a password-protected database on an encrypted computer. Only select trained laboratory personnel will have access to the file. All computer files or printed data used for analysis also will be de-identified. Consent forms and payment forms will be stored in a locked file cabinet separate from data in an office that is locked when not occupied. Participants' confidentiality also is protected by never associating a participant's name with results in any published or otherwise publicly presented report. Demographic information, including information about participants' age, ethnicity, education, marital status and employment status, will be reported using averages and percentages computed over multiple participants and never reported at the level of individual participants.

#### **Observation And Sensitive Information**

N/A

#### **E. Minimizing Risks**

Participants who indicate psychological distress during participation will be provided with several strategies to reduce distress as needed, including, distraction and deep breathing. Staff will conduct a thorough risk assessment with participants who report suicidal ideation or intent.

Any participants who report suicidal ideation or intent will be provided with information and phone numbers for three local options for mental health care: Rutgers University Behavioral Health Care [contact]), Rutgers Health Psychiatry/Psychology Clinic [contact]), and the Rutgers Psychological Clinic in [contact]). In the unlikely event that a participant reports an imminent intent to harm themselves, we will contact Acute Psychiatric Services [contact]).

#### **F. Certificate of Confidentiality**

We have obtained a Certificate of Confidentiality from the National Institutes of Drug Abuse.

#### **G. Potential Benefits to Subjects**

Each of the three treatment conditions in our proposed project are associated with improved cessation outcomes, which may have a long-term positive impact on health and psychological well-being.

#### **H. Provisions to Protect the Privacy Interests of Subjects**

Participants will be asked to engage with trained research staff throughout the course of the study. However, if participants indicate a desire not to work with a particular staff member, we will oblige.

Our research team employs standard procedures to ensure confidential information about study participation is not disclosed. All data are linked to an arbitrary 3-digit study ID unrelated to personal information. The file linking participants to their study ID will be stored in a password-protected file, located within a password-protected database on an encrypted computer. Only select trained laboratory personnel will have access to the file. All computer files or printed data used for analysis also will be de-identified. Consent forms and payment forms will be stored in a locked file cabinet separate from data in an office that is locked when not occupied. Participants' confidentiality also is protected by never associating a participant's name with results in any published or otherwise publicly presented report. Demographic information, including information about participants' age, ethnicity, education, marital status and employment status, will be reported using averages and percentages computed over multiple participants and never reported at the level of individual participants.

#### **I. Research Team Access To Subject Data**

Protocol version: 03.15.2019

PI Name: [name].

Protocol Title: Addressing Tobacco Among  
Public Housing Residents

15

RESERVED FOR IRB STAMP

DO NOT MODIFY THIS SPACE

IRB ID: Pro20170000679

IRB Form Version: y120116

3/25/2019

Expiration Date:

3/24/2020

Only IRB approved staff will have access to participant data. All data will be coded by arbitrary study number to ensure confidentiality and will be stored in a locked filing cabinet or stored on the lab server where access will be password-protected. Data collected online will be de-identified (e.g., associated with an arbitrary study ID number) and only accessible to trained study personnel. Consent forms with identifying information (names) will be filed separately from actual study data in a separate locked filing cabinet. This cabinet the office in which it is kept will ensure that it is also double-locked.

**4.10 Secondary Data – Records/Chart Reviews/Databases/Tissue Banks/etc.**

N/A

**4.11 Chart/Record Review Selection**

N/A

**4.12 Secondary Specimen Collection**

N/A

**5.0 Special Considerations**

**5.1 Health Insurance Portability and Accountability Act (HIPAA)**

N/A

**5.2 Family Educational Rights and Privacy Act (FERPA)**

N/A

**5.3 NJ Access to Medical Research Act**

N/A

**5.4 Code of Federal Regulations Title 45 Part 46 (Vulnerable Populations)**

N/A.

**6.0 Research Data Protection and Reporting**

**6.1 Data Management and Confidentiality**

**A.** Success of randomization will be checked via summary statistics of baseline demographic and psychosocial characteristics. Depending on the measurement scale of each variable, we will use either  $\chi^2$  or independent samples t-tests, corrected for unequal variances if indicated. Variables found to show significant baseline differences between groups will be included as covariates. Logistic regression analyses will be conducted to examine differences in dichotomous outcomes such as abstinence (yes/no), quit attempts (yes/no), and treatment seeking (yes/no). Because this is a small, pilot study, we will report effect sizes representing each of the two active interventions (MI and NRT sampling) as compared to the control intervention (referral only).

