Official Title: Addressing Tobacco in Public Housing Residents

Identifiers: NCT03620708

Document Date: September 27, 2019

Statistical Analysis Plan

To assess for differences in outcomes between groups we will use chi-square for dichotomous outcomes and analysis of variance / analysis of covariance for continuous outcomes. We will consider covariates based on theoretical grounds (e.g., baseline cigarettes per day, baseline motivation to quit, financial disadvantage) and significant differences between groups at baseline. Significant results will be probed using Dunnett's method, whereby our comparison of interest was between the treatment conditions and control condition. We will further report effect size estimates (i.e., f for ANOVA; Cramer's V for chi-square) to help elucidate aspects of the pilot study that may be most beneficial. Data will also be examined based on the assumption of 'missing equals smoking' and carrying the last observation (i.e., baseline data) forward, as a relatively conservative means of handling data for the n=5 participants lost to follow-up. We will refer to additional analyses of imputed data as intent-to-treat (ITT) analyses.

Outcome 1: A self-described "serious" attempt to quit smoking cigarettes since the initial study appointment, measured by the "Quitting Preparation and Actions Questionnaire."

We will use chi-square analysis to examine differences in proportion of the participants randomized to receive the three intervention groups with respect to making a serious quit attempt between the initial appointment and the 1-month follow-up period.

Outcome 2: Self-reported contact with one of two treatment referrals provided at intervention since the time of the initial study appointment

We will use chi-square analysis to examine differences in proportion of the participants randomized to receive the three intervention groups with respect to seeking treatment at either the NJ QuitLine or a NJ Quitcenter (local tobacco dependence treatment clinic) between the initial appointment and the 1-month follow-up period.

Outcome 3: Self-reported cigarettes smoked per day

We will use Analysis of Covariance (ANCOVA) to examine differences in cigarettes smoked per day at the 1-month follow-up between participants randomized to the three intervention groups. Baseline cigarettes smoked per day and measures of motivation to quit will be included as covariates.

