Outcome 4: Motivation and Self-efficacy for quitting smoking measured via Importance, Confidence, & Readiness Questionnaire" (rated on a 0 to 10 scale)

We will use separate Analysis of Covariance (ANCOVA) to examine differences in a) Self-reported Importance of quitting, b) Self-reported Confidence in one's ability to quit, and c) Self-reported Readiness to quit at the 1-month follow-up between participants randomized to the three intervention groups. Baseline ratings of motivation to quit will be included as a covariates.

Outcome 5: "Readiness to Quit Ladder" (with 10 non-numbered choices reflecting varying degrees of readiness

We will use Analysis of Covariance (ANCOVA) to examine differences in cigarettes smoked per day at the 1-month follow-up between participants randomized to the three intervention groups. Baseline score on the Readiness to Quit Ladder will be included as a covariate.

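### A significant baseline difference can bring a covariate into the Outcome 3 to 5 ANCOVAs, so chance imbalance rather than prognosis helps choose the model

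*Protocol*

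**What the plan says.** Protocol section 6.1 A checks the success of randomisation by testing baseline demographic and psychosocial variables between arms. It uses chi-square or "independent samples t-tests, corrected for unequal variances if indicated". It then makes the result binding: "Variables found to show significant baseline differences between groups will be included as covariates". The same paragraph plans regression models to which that rule would apply: "Logistic regression analyses will be conducted to examine differences in dichotomous outcomes".

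The SAP, dated 27 September 2019, is later than the protocol version of 15 March 2019 and is softer. Its general paragraph says "We will consider covariates based on theoretical grounds", gives examples (baseline cigarettes per day, baseline motivation, financial disadvantage), and adds a second ground: "and significant differences between groups at baseline".

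The outcome-specific text names some covariates. For Outcome 3: "Baseline cigarettes smoked per day and measures of motivation to quit will be included as covariates". For Outcome 4: "Baseline ratings of motivation to quit will be included as a covariates". For Outcome 5 it is the baseline Readiness Ladder score. None of these lists is said to be complete, and the general sentence is not limited to particular outcomes. For Outcomes 1 and 2 the SAP uses an unadjusted test: "We will use chi-square analysis to examine differences in proportion of the participants randomized to receive the three intervention groups".

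Neither document lists the variables to be screened or gives the significance level for the baseline tests.

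**The concern.** Allocation is randomised, so if it was carried out properly, a significant baseline difference is a chance event. It carries no information on whether the variable predicts outcome. Adjustment gains precision from prognostic variables and loses precision from variables that are merely imbalanced. The trigger selects for the second property.

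The rule also cannot be run as written. A t-test compares two groups and there are three arms, so an analyst could test each active arm against control, test all three pairs, or substitute a one-way ANOVA. Each choice flags variables at a different rate, and two analysts following the text could fit different models.

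This matters because protocol section 6.1 B says the pilot's data will supply effect sizes for a larger grant application. For Outcomes 3 to 5, the adjusted differences would depend partly on which variables chance happened to flag.

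**Working it through.** **No figure to reproduce.** The plan gives no number that bears on this rule.

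**Inputs from the documents.** 20 per arm, three arms (protocol 1.5). Protocol 1.9 B lists 16 online measures, one of them used only at follow-up, which leaves 15 at baseline.

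**Assumptions.** 15 screened variables. This is a working value: one instrument may yield several variables, and some instruments measure motivation or readiness, which the SAP already adjusts for. Two-sided alpha is 0.05. Every flagged variable is added.

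**1. Chance of at least one flag, independent continuous variables: 1 − (1 − a)^15, where a is the false-positive rate per variable.**

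| Screening test | a | P(at least one) | Expected flags, 15a |
|---|---|---|---|
| One three-arm test | 0.050 | 1 − 0.950^15 = 54% | 0.75 |
| Welch t, each active arm v control | 0.0926 (simulated) | 1 − 0.9074^15 = 77% | 1.39 |
| Welch t, all three pairs | 0.1241 (simulated) | 1 − 0.8759^15 = 86% | 1.86 |

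If about 30% of the list is categorical and tested by one three-group chi-square, the all-pairs figure falls. With 11 continuous and 4 categorical variables it is 1 − 0.8759^11 × 0.95^4 = 81%. Correlation among candidates lowers the chance of any flag but not the expected number. Simulation of the mixed list, with candidates independent or correlated at 0.3, gave 48 to 81% across the three screening tests. A shorter run gave 42 to 81%. A fair summary is roughly 45 to 80%.

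**2. Why an imbalanced covariate costs precision.** With one covariate, the ANCOVA contrast between two arms has variance σ²[2/n + d²/SSW]. Here d is the difference in covariate means and SSW is the within-arm sum of squares, with 60 − 3 = 57 degrees of freedom. Since d² = t² × (2/n) × SSW/57, the variance is multiplied by 1 + t²/57. At the 5% threshold with 38 degrees of freedom, t = 2.02, so a variable that is only just flagged costs 2.02²/57 = 7%. It repays this only if it explains more than 1 − 1/1.07 = 6.5% of the residual variance, a partial correlation of about 0.26.

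**3. Simulated change in contrast variance.** The comparison is one fixed baseline (r = 0.5 with outcome, assumed) against that baseline plus all flagged variables, with the mixed list of 15.
- Candidates not prognostic: about +4% to +10%.
- Candidates correlated at 0.3, five of them prognostic (0.15 each, assumed): −1.3%, +0.5% and +0.8% under the ANOVA, active-versus-control and all-pairs screens. This cannot be told from zero.

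For scale, the 95% half-width with the fixed baseline is about 2.00 × √(0.75 × 2/20) = 0.55 SD. A 10% rise in variance takes it to 0.55 × √1.10 = 0.58 SD.

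**4. Movement of the estimate.** When at least one independent, non-prognostic variable is flagged, the estimate moves by a median of 0.04 to 0.06 SD. In one trial in ten it moves by more than 0.13 to 0.18 SD. These figures include runs at 18 per arm, a rough allowance for the five lost.

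**5. Type I error.** With 8 to 25 variables screened, it was 4.5 to 5.8%. A separate run with 10 candidates, one of them prognostic, gave 5.3% when that candidate's correlation with outcome was 0, falling to 3.6% when it was 0.5. In that run the rule changed the significance verdict in 1.9 to 3.1% of null trials.

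**6. Logistic regression, if used.** At the 50% quit-attempt rate in protocol 1.5 and with 8 to 25 variables screened, the standard error of the arm log odds ratio rose by 2 to 11%. Type I error was 4.4 to 6.0%.

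**The case against.** The strongest reply is that little hangs on this. The SAP is the later document, requires nothing, and puts theory first, so every figure above overstates what an analyst would probably do. Protocol 1.5 calls the quit attempt the main outcome, and the SAP analyses it by chi-square with no covariates. The ANCOVAs already name sensible baselines. The candidates are probably correlated, since protocol 1.9 B says six items are shared between two distress scales. If they are also prognostic, the variance effect is near zero and may be a small gain.

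All of this stands, and it limits the severity. It does not rescue the trigger. A variable thought to be prognostic can be named in advance, which secures the gain whether or not chance flags it. The softer wording also leaves the choice to the analyst without a stated criterion, at a point when the SAP already reports five participants lost to follow-up.

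A reader might infer from that last fact that covariates were chosen after outcomes had been seen by arm. The documents do not show this. They show only that follow-up was at least partly known when the SAP was dated.

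**Conclusion.** The point holds at minor to moderate severity. Both documents let a chance baseline difference bring covariates into the ANCOVAs for Outcomes 3 to 5, and the protocol's version would also apply to its logistic regressions. The consequence is a model that depends on the data, with a modest loss of precision if the flagged variables are not prognostic and no clear effect if they are correlated and prognostic. The size rests on the assumed 15 variables, alpha of 0.05 and 20 per arm, and is an upper bound because it adds every flagged variable.

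Two stronger readings are not supported. One is that the rule makes the tests anti-conservative: simulated Type I error stays near 5% and can fall below it. The other is that it undermines the main result: the SAP's chi-square tests for quit attempts and treatment seeking take no covariates.

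**What to change.** - Delete the baseline-significance trigger from protocol 6.1 A and from the SAP's general paragraph. Describe baseline balance by arm without p-values.
- For each ANCOVA, fix a short list from the covariates the SAP already names: the outcome's own baseline, baseline cigarettes per day, and one named motivation score. State explicitly whether a financial-disadvantage measure is included, and which one, since the SAP cites it on theoretical grounds.
- For Outcome 5, first reconcile the heading, which is the Readiness Ladder, with the analysis text, which refers to daily cigarette consumption. Then use the baseline of whichever outcome is meant.
- Use the same fixed approach in any logistic regression that is kept.
- Date the decision. If outcomes by arm had already been seen, label the adjusted results post hoc.

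The cost is wording in two places and a dated list, with no new data. The downside is that a prognostic variable outside the list, if imbalanced by chance, goes unadjusted in the main analysis. In some correlated and prognostic settings with an all-continuous list, this gives up as much as about 10% in variance. Such a variable can be added in a labelled sensitivity analysis.
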